4 INVESTIGATIONAL PLAN

4.1 STUDY DESIGN

ALVE study is a clinical investigation assessing Alveogyl performance and safety in patients with post-extraction dry socket. The study will take place in India and in France where the study device is already marketed.

In India, the study is regulatorily considered as a pivotal clinical study in accordance with the Indian regulation.

In France – European Union, the study is regulatorily considered as an observational, post-market clinical follow-up study with additional non-invasive and non-cumbersome procedures: the clinical

investigation is under the category “Other Investigation (Case 1: Clinical Investigation Post-Market Clinical Follow-Up)” in accordance with the European Medical Device Regulation (EU MDR).

Management of dry socket application protocol is at the discretion of the Investigator. Patients treated with the study device will be screened and eligible patients will be included in the study after obtaining their consent.

The primary outcome will be pain assessed by Visual Analog Scale (VAS) for adults at 7 days post-treatment. VAS is a 10-point line from “no pain” (0 point) to “worst imaginable pain” (10 points). A corresponding scale will be used for children as appropriate.

Additionally, patients will self-evaluate their pain level, their painkiller use and the feeling of Alveogyl (clove) taste at day 3 and day 5 at home.

All data will be recorded in either paper or electronic Case Report Form (CRF) and monitored by the Sponsor’s designee.

4.2 STUDY DURATION, ENROLMENT AND SITES

4.2.1 Duration of enrolment

Patients’ enrolment will last 30 months (estimate).

4.2.2 Duration of study participation

Each patient will be clinically examined at visit 1 – Day 0 (at the time of positive diagnosis of dry socket and use of Alveogyl) and at 7 days post-treatment (visit 2 – Day 7).

Each patient’s participation will last 8 days.

4.2.3 Number of investigational sites and patients estimated

120 patients will be enrolled in the clinical study.

The clinical study will be conducted at approximately 10 investigational sites in India which should recruit about 90 patients, and at 2 sites in France which should recruit about 30 patients.

4.3 STUDY POPULATION

4.3.1 Inclusion criteria

Patient fulfilling all the following criteria is eligible for the clinical investigation:

- Male or female patient, adult or child
- Positive diagnosis of dry socket occurring after the extraction of a permanent tooth (mature or immature)
- Signed informed consent
- Patients affiliated to a Health Insurance Scheme (“sécurité sociale”)

4.3.2 Exclusion criteria

The presence of any of the following exclusion criteria will lead to the exclusion of the patient:

- Spreading infection in the alveolar socket
- Placement of Alveogyl done immediately after tooth extraction
- Multiple post-extraction dry sockets

- Patient treated with cervico-facial radiotherapy
- Immunodeficiency related to any diseases or current treatments
- Psychiatric patient or patient unable to assess his/her pain via the study Pain VAS
- Patient with history of hypersensitivity to one of the components
- Patient on post extraction of deciduous teeth
- Participation in another clinical investigation

4.4 PATIENT INFORMATION AND INFORMED CONSENT

The Principal Investigator (PI) or designee explains to each patient the nature of the study, its purpose, the procedures involved, the expected duration, the potential risks and benefits and any discomfort it may entail. Each patient is informed that the participation in the study is voluntary and that he/she may withdraw from the investigation at any time and that withdrawal of consent will not affect his/her subsequent medical assistance and treatment. The patients are informed that he/she can ask any question. Time is given to the patients to read and understand the consent form.

The patients are informed that authorised individuals other than their treating physician may examine his/her medical records.

All patients are given a patient information document and a consent form describing the study and providing sufficient information for the patients to make an informed decision about their participation in the study.

The formal consent of a patient, using the approved consent form, is obtained before the patient is enrolled into the study and submitted to any study procedure.

The patient should read, understand, and voluntarily agree before signing and dating the informed consent form, and is given a copy of the signed document. The consent form is signed and dated by the patient and the PI (or her/his designee). The signed consent form is then retained as part of the investigation records.

4.4.1 Minors/underage patients

For minor/underage patients the study's investigator or designee will discuss with the patient's parent or legal representative, who may give his/her informed consent on the patient's behalf. The minor patient will also be informed about the study within his/her ability to understand: a dedicated information sheet will be provided to the minor patient.

4.4.2 Other vulnerable subjects

Other vulnerable patients can be included in the study (i.e. individuals with lack or loss of autonomy due to immaturity or disability, persons in nursing homes, impoverished persons, subjects in emergency situations, ethnic minority groups, homeless persons, nomads, refugees, and persons kept in detention). There is no additional risk nor contraindication for this type of population.

If the patient is unable to make the decision to participate in this study, the study's investigator or designee will discuss with the patient's legal representative.

4.5 STUDY PROCEDURES

4.5.1 Visit 1 – Day 0

During this visit (same day as dry socket diagnostic and procedure of Alveogyl treatment), the following elements will be performed:

- Eligibility criteria: Prior to patients' enrolment into the study, patients' inclusion and exclusion criteria will be reviewed by the investigator.
- Patient informed consent: see §4.4
- Medical record review: which will be extracted from the patients' medical chart (i.e., Date of birth (MM-YYYY), gender, risk factors); medical information related to tooth extraction and dry socket before the procedure (such as date of tooth extraction, numbered of the extracted tooth, etiology of the tooth extracted, ...); Concomitant therapy.
- Clinical signs or symptoms: such as presence of gum infection/periodontitis, time after which the pain started, blood clot within the alveolar socket, halitosis, confirmation of the diagnosis of dry socket, local inflammation evaluation, bleeding evaluation,...
- Visual Analog Scale: pain assessment through the VAS before the procedure

Placement of Alveogyl use is done according to the instruction for use (IFU, Annex 1)

Before inserting the paste, the socket shall be re-examined.

The inside of the socket should be thoroughly cleaned (i.e., irrigated and/or curetted) to remove all debris.

Take a small pellet (about 0.20 g) of paste and place it gently into the prepared dental socket. Do not suture.

Note 1: The management of dry socket paste application protocol is at the discretion of the Investigator, knowing that there are available guidelines (e.g., Canadian Dental Association, 2013).

Note 2: For more details on the procedure of use, precautions and warnings see IFU.

The following information will be collected:

- Clinical signs or symptoms: medical information related to dry socket
- Procedure information: type of pre-Alveogyl treatment (curettage, cleaning, local anaesthesia etc.); feedbacks on the study device (manipulation, consistency, placement); Post-Alveogyl treatment information (local inflammation evaluation, bleeding evaluation,...)
- Visual Analog Scale: pain assessment through the VAS after the procedure

4.5.2 Follow-up visit (Visit 2 – Day 7)

During patients' follow-up visit at 7-day post-treatment, the following elements will be evaluated:

- Clinical signs or symptoms: medical information related to dry socket (local inflammation evaluation, infection of the studied socket, healing evaluation, presence or not of Alveogyl paste in the socket,...)

- Serious and non-serious adverse events and Alveogyl deficiency since Visit 1 (See §6.3)
- Visual Analog Scale: pain assessment through the VAS
- Painkiller use

Additionally to the clinical follow-up visit at 7-day post-treatment, patients have to complete at home a form at Day 3 and Day 5 post-treatment with the following information to collect:

- Visual Analog Scale: pain assessment through the VAS
- Presence or not of Alveogyl clove taste feeling
- Painkiller use

4.5.3 Unscheduled visits

Patients may come back before the scheduled visit at 7 days post-treatment for various reasons (e.g., pain, other adverse events). In this case, the following information will be recorded in the study CRF:

- Date of the visit
- Reason of the visit
- Clinical signs or symptoms: medical information related to dry socket (local inflammation evaluation, infection of the studied socket, healing evaluation, presence or not of Alveogyl paste in the socket,...)
- Type of treatment if applicable and information on whether if Alveogyl was re-used during the visit.

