5.4.1 Analysis populations

Included population (intention-to-treat population - ITT): all included patients.

Evaluable population (per-protocol population - PPP): all patients from the included population with no exclusion criteria and with VAS available at Day 7.

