5.4.3 Analysis of Primary endpoint

The primary endpoint is the binary variable (yes / no) defined as the VAS at Day 7 < 4 (i.e., "Yes" when VAS is <4, "No" when VAS is \geq 4).

It will be reported with a percentage and a 95% confidence interval (with the exact method) in the evaluable population.

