5.4.4 Analysis of Secondary endpoints

The secondary analyses will consist of:

- Evolution of VAS from the day (D0) of use of Alveogyl to 7 days post treatment. Summary statistics of VAS will be provided at Day D0, D3, D5 and D7 in available observations (no imputation for missing values will be made). For each timepoint, difference with measure at D0 will also be calculated.
- The complication rate will be calculated: number and proportions of the events (quoted in §1.5.2) occurring post treatment
- Description of the clinical signs at D7 and at intermediary visits (if any) to measure the impact of Alveogyl treatment on healing, on antiseptic effect, on local inflammation, and on hemostasis: number and proportions.
- The use of painkillers at D3 and at D7 will be described.
- A listing of the adverse events (AE) will be provided organized by type of AE (Adverse Event ; Adverse Effect related to Alveogyl ; Deficiency of Alveogyl ; Other type or Unknown)

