6.2 SAFETY DATA RECORDING

From the "Visite 1 - Day 0" date until patient end of study (i.e., withdrawal/end of follow-up/lost to follow-up), all adverse events (serious and non-serious), exposure during pregnancy and device deficiencies that occur will be fully investigated, recorded and classified by the Investigator in line with the definitions provided in the norm ISO14155:2020 and guideline MEDDEV 2.7/3.

Investigators will check patients file during clinical follow-up visit and ask patients if they experienced any complications since the index procedure / last visit.

Safety data will be reported in the Case Report Form.

Documentation of AEs (including SAEs) by the PI includes diagnosis or symptoms, start and stop dates of event, event treatment, event resolution, assessment of seriousness and causal relationship to Medical Device and/or investigation procedure (ISO14155).

Documentation of DDs by the PI includes description of event, start date, investigational device information, action taken with regard to the investigational device, and whether the DD led to an AE. The Sponsor shall review all DDs and determine and document in writing whether they could.

The Sponsor provides the Competent/Regulatory Authority (CA/RA) (if applicable) and the Ethic Committee (EC/IRB) with the documentation at their request.

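### As section 5 of the protocol stands, a patient given another socket treatment before Day 7 counts as a success if Day 7 VAS is below 4, and no analysis there links that treatment to the primary rate

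*Combined protocol and SAP*

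**What the plan says.** - **Early returns are foreseen.** Section 4.5.3: "Patients may come back before the scheduled visit at 7 days post-treatment for various reasons (e.g., pain, other adverse events"). The items recorded at such a visit include "Type of treatment if applicable and information on whether if Alveogyl was re-used during the visit". Because re-use of Alveogyl is asked about alongside the type of treatment, treatments other than Alveogyl are evidently expected.
- **Success depends on one measurement.** Section 5.4.3: "The primary endpoint is the binary variable (yes / no) defined as the VAS at Day 7 < 4". It is reported as a percentage with an exact 95% confidence interval in the evaluable population.
- **Re-treatment does not remove a patient.** Section 5.4.1 defines the evaluable population as "all patients from the included population with no exclusion criteria and with VAS available at Day 7". None of the exclusion criteria in section 4.3.2 concerns treatment after placement.
- **Use of unscheduled-visit data.** Section 5.4.4 plans a "Description of the clinical signs at D7 and at intermediary visits (if any"). It does not mention the treatment given at those visits.
- **Safety outputs.** Section 5.4.4: "The complication rate will be calculated: number and proportions of the events" listed in section 1.5.2, where pain appears, together with an adverse event listing by type. Section 6.2: "Documentation of AEs (including SAEs) by the PI includes diagnosis or symptoms, start and stop dates of event, event treatment".
- **Separate plan.** Section 5.4 announces a separate statistical analysis plan, which is not among the documents.

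**The concern.** The primary objective (section 3.1.1) concerns the effect of Alveogyl on pain at Day 7, and section 1.3 lists pain reduction among the manufacturer's claims that the study is to verify. The protocol describes no comparator. If the first placement fails to control pain and a different socket treatment then does, the relief appears in the VAS<4 rate as though Alveogyl had produced it, and no control arm offsets this.

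The patients concerned are those in whom the device, by itself, had not yet worked. Provided the other treatment did not make pain worse, counting them as successes can only raise the rate above what would have been seen without that treatment. Section 1.1 gives the study a pivotal role for registration in India and an evidential role for CE-marking under the MDR, so readers of the rate will want to know how many of the successes also had other socket treatment.

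**Working it through.** **1. The plan's own figure.** Inputs from section 5.2: p = 0.92, half-width 0.05, 95% confidence. The normal-approximation formula gives n = p(1−p)(z/0.05)² = 0.92 × 0.08 × (1.96/0.05)² ≈ 113.1. At n = 113 the half-width is 1.96 × √(0.92 × 0.08/113) = 0.0500. The stated 113 reproduces, and 113 + 7 = 120.

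**2. How one patient is classified.** Suppose a patient returns in pain on Day 3, has a non-Alveogyl treatment of the socket and scores 2 on Day 7.
- Section 5.4.1: Day 7 VAS available and no exclusion criterion, so evaluable.
- Section 5.4.3: 2 < 4, so 'Yes'.
- Section 5.5: covers only missing data, so it changes nothing.

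**3. Does any analysis in section 5 show this beside the rate?**

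| Planned output (5.4.4) | Uses treatment at unscheduled visit? | Linked to the primary outcome? |
|---|---|---|
| VAS at D0, D3, D5, D7 | No | No |
| Complication rate | No (counts events) | No |
| Clinical signs at D7 and intermediary visits | No | No |
| Painkiller use | No | No |
| Adverse event listing by type | Not named, although event treatment is documented under 6.2 | No |

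The return itself may be visible in several of these outputs. The number of primary successes who had other socket treatment is not.

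**4. Size.** The documents give no re-treatment rate. Let k be the number of VAS<4 patients who had other socket treatment; re-treated patients with VAS of 4 or more are already 'No'. Each one moves the rate by 1/113 = 0.88 points. The planning assumption corresponds to 104/113, since 0.92 × 113 ≈ 104. With Clopper-Pearson 95% intervals for (104 − k)/113, every k being assumed:

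| k | Counted 'Yes' | Rate | Exact 95% CI | Width (points) |
|---|---|---|---|---|
| 0 | 104/113 | 92.0% | 85.4 to 96.3 | 10.9 |
| 1 | 103/113 | 91.2% | 84.3 to 95.7 | 11.3 |
| 3 | 101/113 | 89.4% | 82.2 to 94.4 | 12.2 |
| 6 | 98/113 | 86.7% | 79.1 to 92.4 | 13.3 |

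For scale, the planned half-width of 5 points equals 0.05 × 113 = 5.65 patients, so k = 6 shifts the estimate by 6/113 = 5.3 points, slightly more than the planned precision.

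**5. What the supplementary rate bounds.** Counting the k patients as 'No' assumes that none of them would have reached VAS<4 without the other treatment. Some might have. Within the evaluable population, and if the other treatment did not worsen pain, that rate is therefore a lower bound on the success rate without other treatment. Its gap from the primary rate, k/113, is an upper bound on the overstatement.

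**The case against.** The strongest reply is that nothing is misclassified. Sections 5.4.1 and 5.4.3 together fix a rule in advance: the Day 7 score counts whatever happens in between. For a marketed device used in routine care, with the application protocol left to the investigator (section 4.1), that is a legitimate target. This stands. A reader might infer that the primary rate is wrong or that these patients should be excluded; the documents support neither. The issue is only how far the rate can be attributed to Alveogyl.

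Second, the SAP may already cover this. That also stands, and it limits the finding to section 5 of the protocol. It cannot be said that no analysis is planned anywhere.

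Third, little turns on the number. There is no performance threshold or test, so no decision can flip. Attribution is already limited by natural resolution and by the preparation of the socket, for which section 4.5.1 says "The inside of the socket should be thoroughly cleaned (i.e., irrigated and/or curetted) to remove all debris". This is true, and the supplementary rate removes neither. Other socket treatment, however, is a source that the study intends to record, so leaving it unreported is avoidable.

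Fourth, returns for pain are not hidden: they can appear in the complication rate, the event listing, the Day 3 and Day 5 VAS, and the signs at intermediary visits. Agreed; what is missing is the cross-link to the primary outcome.

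Fifth, a reader might assume that all care between Day 0 and Day 7 is captured. It is not clearly so. Treatment is recorded at unscheduled visits (4.5.3) and for adverse events (6.2), while Table 1 schedules concomitant medications only at Visit 1. The CRF is not shown. This stands and narrows what the fix can deliver.

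**Conclusion.** The point holds for section 5 as written. A patient with other socket treatment before Day 7 and a Day 7 VAS below 4 is a success, and no analysis in that section ties the recorded treatment to the primary rate. The rate remains valid as an outcome regardless of further treatment. As a measure of relief attributable to Alveogyl it can be too high, by at most 0.88 points per such patient at n = 113.

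The total is unknown. k = 0 is as compatible with the documents as k = 6, so the table above is no evidence that the rate will in fact be inflated. The direction rests on the assumption that the other treatment did not worsen pain. The bound covers only recorded treatment in evaluable patients. Treatment obtained elsewhere and not recorded lies outside it, as do patients withdrawn under section 4.5.4 without a Day 7 VAS. This is a worthwhile, inexpensive improvement to the reporting of the primary result.

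**What to change.** In section 5.4.3, or in the SAP if that is where the detail will sit:

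1. Keep the VAS<4 rate in the evaluable population as primary, and state that it is regardless of further treatment.
2. Add a supplementary rate in the same population, with exact 95% CI, that counts as 'No' any patient with a non-Alveogyl socket treatment recorded at an unscheduled visit (4.5.3) or as adverse event treatment (6.2) before the Day 7 VAS. Irrigation, curettage or local anaesthesia done to prepare a repeat Alveogyl placement does not count as other treatment.
3. Add a second row that also counts Alveogyl re-use as 'No'.
4. Report the numbers with other treatment and with re-use beside the primary rate.
5. State the limits: unrecorded treatment elsewhere and patients without a Day 7 VAS are not covered. Analgesic use stays a separate secondary endpoint.

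The cost is a few sentences and two table rows; endpoint, population and sample size do not change. The sponsor should check that the CRF separates preparatory cleaning from stand-alone treatment. The downside is that the supplementary rate may be lower and less precise (interval width 13.3 points at k = 6 against 10.9 at k = 0). If k = 0, the first supplementary rate equals the primary rate and shows that no recorded treatment of this kind affected it. If the SAP already contains this, confirming it is enough.

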4.5.4 Patient completion/Withdrawal

Patients may withdraw from the study at any time without prejudice to their care. They may also be discontinued from the study at the discretion of the Investigator for lack of adherence to study treatment or visit schedules or AEs.

The Investigator may also withdraw patients who violate the study plan, or to protect the patients for reasons of safety or for administrative reasons. It will be documented whether each patient completes the clinical study. If the Investigator becomes aware of any serious, related adverse events after the patient completes or withdraws from the study, they will be recorded in the source documents and on the CRF.

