5.5 HANDLING OF MISSING DATA AND DROP-OUTS

No data will not be imputed, only available data will be used in the analyses.

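### Investigator withdrawal for adverse events or safety ends Day 7 data collection, which can bias the primary success percentage upward and truncates the safety record

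*Combined protocol and SAP*

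**What the plan says.** Section 4.5.4 gives the Investigator two sets of grounds for ending a patient's participation. Patients may be "discontinued from the study at the discretion of the Investigator for lack of adherence to study treatment or visit schedules or AEs". In addition, "The Investigator may also withdraw patients who violate the study plan, or to protect the patients for reasons of safety or for administrative reasons". The section requires a record of whether each patient completed the study. It does not ask for the reason when a patient did not, and it does not ask for a Day 7 assessment after discontinuation.

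The analysis rules then apply:

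- Section 5.4.3: "The primary endpoint is the binary variable (yes / no) defined as the VAS at Day 7 < 4". The result is planned as follows: "It will be reported with a percentage and a 95% confidence interval (with the exact method) in the evaluable population".
- Section 5.4.1 defines that population as "all patients from the included population with no exclusion criteria and with VAS available at Day 7".
- Section 5.5: "No data will not be imputed, only available data will be used in the analyses". The first half is a double negative, but the second half makes the intention clear.

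The included population is used for baseline description (5.4.2). No analysis of the primary endpoint in it is stated.

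For safety, section 6.2 opens recording at Visit 1 and runs it "until patient end of study (i.e., withdrawal/end of follow-up/lost to follow-up), all adverse events (serious and non-serious"), so withdrawal closes the window. What remains afterwards is the last provision of 4.5.4: "If the Investigator becomes aware of any serious, related adverse events after the patient completes or withdraws from the study, they will be recorded". Section 3.2.2 defines the complication rate from placement to 7 days.

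**The concern.** The wording in 4.5.4 concerns leaving the study, not stopping a treatment. Table 1 plans one placement on Day 0, followed by two home forms and one visit. A patient discontinued by the Investigator therefore loses the Day 7 VAS unless someone chooses to collect it, and without that score drops out of the only stated primary analysis.

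This missingness may well depend on outcome. Section 1.5.2 lists pain, infection, swelling, local inflammation and delayed healing as anticipated adverse events. Pain is thus both a possible ground for withdrawal and the quantity being measured. Section 4.5.3 expects some patients to return early because of pain or other adverse events, but its list of items to record has no VAS, so an early visit need not leave a pain score behind. Section 4.1 describes no comparator, so there is no second arm in which a similar loss might partly cancel.

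The study is classed as pivotal in India (4.1) and is meant to support CE-marking under the MDR (1.1). Its sample size rests solely on estimating one percentage to within 5 points, so a bias of a few points matters.

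**Working it through.** **Inputs.** Expected success 0.92, half-width 0.05, 113 evaluable patients and 7 added for non-evaluability (5.2); 120 enrolled (4.2.3); exact 95% interval in the evaluable population (5.4.3). The plan gives no expected number of withdrawals for adverse events, so that number is varied as an assumption.

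**Step 1: reproduce the plan's figure.** n = z² p(1 − p)/d² = 1.96² × 0.92 × 0.08 / 0.05² = 113.09. The stated 113 reproduces, and 113 + 7 = 120.

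**Step 2: observed rate near 92%, missing patients assumed to be failures.** Let k of the 120 have no Day 7 VAS, and let x be 92% of the remaining 120 − k, rounded. The plan reports x/(120 − k). If all k were failures, the rate in everyone is x/120.

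| k | Reported | All k are failures | Gap (points) |
|---|---|---|---|
| 0 | 110/120 = 91.7% | 110/120 = 91.7% | 0 |
| 3 | 108/117 = 92.3% | 108/120 = 90.0% | 2.3 |
| 5 | 106/115 = 92.2% | 106/120 = 88.3% | 3.8 |
| 7 | 104/113 = 92.0% | 104/120 = 86.7% | 5.4 |

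At k = 7 the exact intervals are 85.4% to 96.3% (104/113) and 79.3% to 92.2% (104/120). If all seven were instead successes, the rate would be (104 + 7)/120 = 92.5%. The seven missing scores therefore leave the full-cohort rate anywhere from 86.7% to 92.5%, and nearly all of that range lies below the reported 92.0%.

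**Step 3: the same mechanism from the other side.** Assume the full result is 110/120 = 91.7%, with 10 failures, and that only failures are withdrawn. One withdrawal gives 110/119 = 92.4%, three give 110/117 = 94.0%, and seven give 110/113 = 97.3%. Each lost failure adds about 0.8 points. In the extreme case of seven, the exact interval is 92.4% to 99.4%, which excludes the assumed 91.7%.

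**Step 4: the safety record.** No arithmetic is possible, because the documents give no event rate after withdrawal and 5.4.4 states no denominator for the complication rate. The provisions compare as follows:

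- Up to and including the event that prompts withdrawal: all adverse events are recorded (6.2).
- From withdrawal to Day 7: only events that are both serious and related, and only if the Investigator learns of them (4.5.4).
- Window of the endpoint: placement to 7 days for every patient (3.2.2).

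In withdrawn patients the gap is later non-serious events and later unrelated serious events.

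**The case against.** The strongest reply is that the plan does not send patients who do badly out of the study. Withdrawal is permitted, not required. Several grounds, such as missed visits and administrative reasons, need not track pain. Section 4.5.3 gives patients who return with pain an on-study route: they are examined, treatment is recorded, and the Day 7 visit can still take place. This stands. A reader might infer that the rule removes precisely the failures and therefore certainly inflates the result; the text supports only that it can remove likely failures.

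A reader might also infer that the safety result is inflated in the same way. The documents do not show that. The triggering event and all earlier ones are recorded, serious related events remain recordable afterwards, and 5.4.4 does not restrict the complication rate to the evaluable population. The record is truncated, but no direction or size of error can be demonstrated.

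It can further be said that study exit may serve a purpose, since 4.5.3 foresees that Alveogyl may be used again at an unscheduled visit. That is fair, but a decision about further use does not require ending data collection.

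Finally, an analysis in all included patients can bound the loss, and 5.4 announces a separate statistical analysis plan in which one might appear. Both points hold. The text under review states no such analysis, however, and a bound is weaker than the Day 7 score itself.

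**Conclusion.** The point holds in conditional form. As written, 4.5.4 together with 5.4.1, 5.4.3 and 5.5 allows patients with adverse events to leave the primary analysis without trace, and this can bias the success percentage upward. The size is 0 if withdrawals are unrelated to pain, 2.3 points with three withdrawn failures and 5.4 points with seven. The last figure is a worst case: the seven are an allowance for non-evaluability of any cause, and all would have to be failures. It is nonetheless about as large as the whole planned precision of 5 points. If more than seven patients lacked a Day 7 score, the gap could be larger.

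On safety, the conclusion is limited to incompleteness: non-serious events and unrelated serious events between withdrawal and Day 7 are not collected, although the endpoint covers that period.

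The change should be made, because missing Day 7 scores cannot be recovered afterwards.

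**What to change.** - **4.5.4:** separate decisions about care from the end of data collection. The existing grounds for discontinuation can stay. State that a patient discontinued by the Investigator who has not withdrawn consent is still followed to Day 7 for VAS, painkiller use, clinical examination and adverse events. Record the reason for every discontinuation.
- **6.2:** extend adverse event recording to Day 7 for every treated patient who has not withdrawn consent.
- **5.4.3:** add an analysis of the primary endpoint in all included patients, counting a missing Day 7 VAS as non-success. It belongs beside the planned analysis as a lower bound, since it understates success when scores are missing for reasons unrelated to pain.
- **5.4.4:** state the denominator of the complication rate.

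The cost is mainly amendment wording, with ethics submission in both countries if the change counts as substantial (7.2.1). No patients or visits are added, because Visit 2 is already planned for everyone. Section 13 has the sponsor support data collection and transport for that visit, though not a consultation needed for the patient's own care. The reported success rate may be lower.
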